The proposed sample size is 6,000 participants drawn from 100 worksites. This sample size is larger than previous studies that use incentives or commitment contracts for smoking cessation. For example, the sample size is more than double all but one study included in a recent systematic review of competitions and monetary incentives for smoking cessation.¹³

A preliminary survey of 37 firms who attended a workshop in September 2011 indicated that the median firm has 800 employees, roughly 20% of whom smoke. Of the 37 firms, 35 (95%) expressed an interest in joining the project, implying that the target of recruiting 100 worksites is feasible. Based on the survey data and the pilot study, we expect trial take-up to vary from 10% of smokers in the control arm to 70% in the larger individual bonus arm, and quit rates conditional on take-up to vary from 20% in the control arm to 45% in the deposit contract with a team bonus.

Using Optimal Design Software,⁵³ we computed the minimum detectable effects for a binary abstinence measure as a function of a cluster-randomized binary treatment using a multi-level equation (person at level 1, worksite at level 2) with a random effect for each worksite. We estimated that we will be able to detect absolute differences of at least 7.5 percentage points in abstinence rates for pairwise comparisons between any of the incentive-based arms versus the usual-care control group. This calculation assumed an abstinence rate of 6.0% in the control group (10% conditional on 60% program take-up), 60 participants per worksite, Type-I error $\alpha = 0.05$, and 80% power ($\beta = 0.20$).

Our reported detectable effect sizes are conservative in that they do not adjust for stratification variables used for firm-level randomization (i.e., firm size, industry type, and smoking prevalence) or baseline control variables, both of which will reduce the variance of parameter estimates and, thus, the detectable effect size.

b. Planned statistical analyses

We will conduct descriptive analyses as components of standard data analyses. To evaluate balance across groups achieved by randomization, baseline values of all control variables will be compared across the 9 arms using *t*-tests.

We will use generalized linear mixed-effects models to estimate the intent-to-treat effect of each arm and each intervention component on program take-up and smoking abstinence. The generalized linear mixed-effects models will include a logit link for the binary outcome and a random intercept at the worksite level to adjust for the clustering of participants within a worksite. The primary outcome variable will be verified abstinence, treating reported NRT or e-cigarette use for cessation as abstinent as long as no cigarettes were used. We will report risk

differences from unadjusted and adjusted models. The adjusted models will include prespecified variables known to be related to the outcomes, including baseline demographic characteristics and smoking history. Demographic characteristics will include age (18-25, 26-35, 36-45, ≥ 45), gender, household income per capita, educational attainment (0-3, 4-6, 7-12, ≥ 13 years), marital status (married, not married), any children, and place of childhood (urban Thailand, rural Thailand, foreign country). Smoking characteristics will include average cigarettes per day, moderate-to-high nicotine dependence (Fagerström Test for Nicotine Dependence score ≥ 5), number of past quit attempts, number of years since initiating smoking, and quit intentions (want to quit within 3 months or not).

In sub-analyses, we will pool Groups 2-9 to compare the average effect of receiving usual care plus any incentive program, compared with usual care (Group 1), using similar adjusted and unadjusted mixed-effects models to those described above. We will also investigate interaction effects between intervention components, using the same adjusted mixed-effects models as above. We will also investigate whether those in a bonus group or deposit group are more likely to relapse following the end of the incentive period.

We will perform four sensitivity analyses to assess the robustness of the estimated intervention effects. First, we will conduct the analysis on a per-protocol basis, that is, among those who had accepted their assigned intervention. Second, we will use complete outcome data without assuming that missing cases had smoked. Third, we will exclude from the analysis the outcome data from participants who reported currently using NRT or e-cigarettes. Fourth, we will perform multiple imputation using chained equations to impute missing outcome data at each end point.

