1. Compile contact information for companies located in the targeted industrial areas.

2. During a phone conversation, give a brief introduction and request a brief in-person meeting to discuss the project.
3. Send a letter with the formal request to meet to the appropriate company official as an email attachment.
4. Attend an initial meeting at the worksite as an opportunity 1) to encourage the company officer to join the study and 2) to collect information about challenges and opportunities for recruitment at the company.
5. Hold a workshop to present additional information about the study to officials from worksites that agree to participate in the study.

b. Recruitment of participants

The recruitment of participants will occur in two batches of roughly 50 worksites each. The second batch will begin the intervention approximately three months following the start of the first batch. The staggered approach is designed to relieve some of the pressure on the field teams of having to be active in 100 worksites at once. It will also allow for minor changes in logistical planning to be adopted in Batch 2.

Prior to recruitment of participants, field personnel will make outreach visits to each worksite. During these visits, field personnel will set up a booth in a central location at the company, such as in the cafeteria during lunchtime, where they will provide information about the study and answer any questions.

The recruitment of participants at each company will proceed in three phases:

1. Identify all smokers who work at the company during a screening survey. Human resources and/or the health officer will assist with disseminating and collecting the screening surveys.
2. Conduct a baseline survey of all smokers who are eligible for the study, as determined in the screening survey.
3. Invite everyone who is eligible for the study to enroll as a participant in the study. We will send an invitation letter to each person, post flyers and posters around the worksite, and ask the health officer to assist with recruitment.

3. Interventions

The proposed study employs a cluster randomized controlled design with a 3-month intervention followed up 3, 6, and 12 months after enrollment. We will randomly assign participating worksites to treatment arms that vary on three cross-randomized components: 1) deposits or no deposits, 2) bonus size (none, small, large) and 3) teammate or individual.

a. Intervention components

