After providing a urine sample, each participant will complete a short survey administered by study personnel on a portable tablet. A separate module will be administered for self-reported quitters and self-reported continuing smokers, as determined at the start of the questionnaire. All respondents will be asked questions related to smoking behavior and quit attempts since the prior meeting. Participants will also be asked additional questions about their behavior during the intervention period and their perceptions related to the intervention.

At the end of the follow-up visit, each participant will receive an inconvenience gift worth 150 baht. Participants may choose to be paid in cash or in kind.

A field team member will contact by phone the participants who do not attend the follow-up visit to ascertain their self-reported smoking status. The reason for non-attendance will be recorded. If a participant reports having abstained, a field worker will schedule a time within the next 48 hours to provide a urine sample for biochemical verification. Those who provide the urine sample will receive the inconvenience gift worth 150 baht.

5. Randomization

After baseline surveys are completed, worksites will be randomly assigned in equal proportion to one of the nine randomization groups. The cluster randomized design mitigated concerns of within-worksite contamination and is expected to be viewed by employers as more acceptable than person-level randomization. We will follow a covariate-adaptive procedure, in which we will minimize the *p*-value from a joint *F*-test as a balance criterion implemented over 1,000 iterations.⁵⁰ In Monte Carlo simulations, minimization has been found to facilitate covariate balance.⁵¹ The randomization procedure will include the following worksite-level covariates, which we will also include in the adjusted regression analyses: province, mean age, mean proportion born in Thailand, mean cigarettes per week, mean proportion who want to quit smoking within 6 months, number of employees, and estimated smoking prevalence based on baseline data.

A study investigator will implement the random allocation sequences using computer-generated random numbers, concealing the sequence from field staff, company employees, and participants until after the baseline survey has been completed. Participants will be informed of their assignment in an enrollment invitation letter sent following the baseline survey.

6. Outcomes

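### The allocation rule in D.5 keeps the draw with the smallest joint F-test p-value out of 1,000, which is the worst-balanced draw on that criterion

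*Combined protocol and SAP*

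**What the plan says.** Section D.5 (Randomization) is the only place that specifies the allocation. Worksites go in equal proportion to nine groups by a covariate-adaptive procedure that will "minimize the *p*-value from a joint *F*-test as a balance criterion implemented over 1,000 iterations". The next sentence gives the purpose: "In Monte Carlo simulations, minimization has been found to facilitate covariate balance". Seven worksite-level covariates are named: province, mean age, proportion born in Thailand, mean cigarettes per week, proportion wanting to quit within 6 months, number of employees, and smoking prevalence. Of these the section says "which we will also include in the adjusted regression analyses".

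Section D.8.b describes the models: "The adjusted models will include prespecified variables known to be related to the outcomes, including baseline demographic characteristics and smoking history". The variables it then lists do not include province, number of employees or smoking prevalence. It will report risk "differences from unadjusted and adjusted models" and does not say which is primary. It also plans a balance check in which "baseline values of all control variables will be compared across the 9 arms" by t-tests.

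Section D.2.b adds: "The recruitment of participants will occur in two batches of roughly 50 worksites each". D.5 does not say whether the allocation procedure is run once or once per batch.

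**The concern.** The null hypothesis of a joint F-test of balance is that the covariate means are equal across arms. The p-value falls as F, and so the imbalance, rises. Searching 1,000 candidates for the smallest p therefore searches for the largest imbalance. The rule and its stated aim contradict each other, and a programmer who followed the sentence would get less balance than from a single unrestricted draw.

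The target is 100 worksites in nine arms, or 100/9 ≈ 11 per arm. With so few units, chance imbalance is already appreciable, and an allocation cannot be redone once carried out. The stake is extra variance and inflated error in the unadjusted comparisons. It is not systematic bias, because the rule does not favour any arm.

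**Working it through.** The documents give no balance figure to reproduce, so the check is of direction first and size second.

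**Direction.** If the p-values of 1,000 random candidates are roughly uniform, the smallest has expectation 1/1001 = 0.0010 and the largest 1000/1001 = 0.9990. The smallest p is the largest F. This does not depend on any covariate assumption.

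**Size, by simulation.**
- From the documents: 100 worksites (D.2.a), nine arms in equal proportion, seven covariates and 1,000 candidates (D.5).
- Assumed, because the documents do not say: four province levels (three indicators), six independent normal covariates, and a Pillai-trace joint F-test. This gives nine covariate columns.
- 600 to 800 replicates, each with 40 null outcomes, analysed by a linear model of worksite means. This stands in for the logistic mixed model of D.8.b.

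| Quantity | As written | One plain draw | Reversed |
|---|---|---|---|
| Median joint p of the draw kept | 0.001 | 0.49 | 0.999 |
| Mean absolute arm-vs-control difference (SD) | 0.42 | 0.34 | 0.25 |
| Average largest difference (SD) | 1.33 | 1.06 | 0.81 |
| Worksite-level t-tests with p < 0.05, of 8 × 9 = 72 | 8.2 | 3.4 | 0.6 |
| Unadjusted type I error, 10% of worksite-mean variance explained | 5.6% | about 5% | 4.6% |
| Same, 45% explained | 8.3% | about 5% | 2.8% |
| Same, 60% explained | 9.6% | about 5% | 2.2% |
| Adjusted for all seven covariates | about 5% | about 5% | about 5% |

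Repeat runs with separate code gave, for the written rule unadjusted, 5.6% to 5.9% at 10% explained, 6.4% at 20%, 8.0% to 8.3% at 45%, and 9.2% to 9.5% at 60%.

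**Hand check of the unadjusted error.**
1. The ratio of mean differences is 0.42/0.34 = 1.235, so the covariate part of the variance of a difference is multiplied by about 1.235² = 1.526.
2. A plain draw puts 8/99 = 0.081 of the covariate sum of squares between arms. The written rule puts 0.081 × 1.526 = 0.123 there. The within-arm part, which supplies the standard error, shrinks by (1 − 0.123)/(1 − 0.081) = 0.954.
3. With a share R of variance explained, true variance over estimated variance is [1 + 0.526R] / [1 − 0.046R].
4. At R = 0.45 this is 1.237/0.979 = 1.263, with square root 1.124. The two-sided 5% critical value on 91 degrees of freedom, 1.986, acts as 1.986/1.124 = 1.77, giving an error of 8.1%.
5. At R = 0.10 the same steps give 1.053/0.995, square root 1.028, and 5.7%. Both agree with the simulation.

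**Adjusted models.** With all seven covariates, the spread of the estimate under the written rule is about 3% to 4% above a plain draw and about 6% above the reversed rule. If province, number of employees and prevalence were left out, the error under the written rule would be 5.4%, 7.3% and 8.3% at 10%, 45% and 60% explained. The mean estimated difference is about 0, so there is no bias.

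**Other forms.** Separate allocation in two batches of 50 (45% explained) gives 0.41 SD, 7.7% unadjusted and 5.0% adjusted. Two other forms of the joint F-test give 0.38 to 0.40 SD and 6.9% to 7.2% unadjusted. The direction is the same in each.

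**The case against.** The strongest reply is that this is a slip and would not be executed. The sentence itself calls the p-value a balance criterion, the next sentence names balance as the aim, and the reference cited for the rule is titled as a paper on improving covariate balance. The text also does not say outright that the single extreme draw is kept. A slip is indeed plausible. But keeping the extreme draw is the natural reading of minimizing over 1,000 iterations, any rule that prefers small p prefers imbalance, and this is the only specification an implementer has.

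Second, D.5 already promises to adjust for all seven covariates, and the list in D.8.b is open-ended. Read together, the planned adjusted models are protected. This stands: the reduced-adjustment figures describe a departure from D.5, and completing the list is editorial. It does not protect the unadjusted results, which are also to be reported with neither model named as primary.

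Third, the 45% and 60% rows are high. By a standard cluster calculation with 11 worksites per arm, the inputs in D.8.a (6% control rate, 60 per worksite, 80% power, 7.5-point detectable difference) imply an intraclass correlation of about 0.025. The share of worksite-mean variance that is truly between sites is then 0.025/(0.025 + 0.975/60) = 0.61. Explaining 45% of the total would need 0.45/0.61 = 74% of the between-site variance, and 60% would need about 99%. At an intraclass correlation of 0.055, the upper end if the control-arm variance is used for both arms, the share is 0.78 and the needs are 58% and 77%. The 10% row needs only 13% to 17%. This stands too: the lower rows, 5.6% to 6.4%, are the more credible.

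Fourth, the 72 t-tests are on simulated worksite columns, whereas the controls listed in D.8.b are mostly person-level, so that count is not a forecast of the planned check. That check could also reveal a literal execution. Both remarks are fair.

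**Conclusion.** The concern holds. As written, the rule selects the worst-balanced of 1,000 candidates on its own criterion and does worse than plain randomization: 0.42 against 0.34 SD mean absolute difference, where the reversed rule would give 0.25 SD. The direction is certain. The sizes are illustrative and rest on the assumed covariate distributions and form of F-test.

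The consequence for inference is moderate. Unadjusted per-comparison error is about 5.6% to 6.4% if covariates explain 10% to 20% of worksite-mean variance, and 8% to 10% only under high assumptions. Fully adjusted models keep about 5% with a small loss of precision. There is no bias towards any arm. Whether the trial was affected is unknown, because the documents do not show the program. This should be fixed: it is an operative instruction that defeats its stated purpose.

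**What to change.** - In D.5, state that of 1,000 candidate allocations the one with the **largest** joint F-test p-value (smallest F) is used. Define the F-test for nine arms and say whether it is run per batch.
- Confirm the direction in the allocation program. Some past-tense wording in the document suggests that allocation may already have happened. If so, report which rule was run; if it was the literal one, rely on the covariate-adjusted models.
- Add the D.5 worksite covariates to the list in D.8.b, and say which model is primary. The corrected rule makes unadjusted tests conservative (2.8% at 45% explained, 4.6% at 10%), which is a further reason to make the adjusted model primary.

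Cost: before allocation, one sentence and one line of code; afterwards, a program check and one reporting sentence. Completing D.8.b is a further line or two. No added participants or procedures.

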Among worksites assigned to a teammate arm (Arms 3, 5, 7), study personnel will announce pairings. If a participant's teammate did not attend the meeting, study personnel will tell the person that he or she will be randomly assigned to another partner, and study personnel will contact the participant by phone within the next few days to inform him or her of the teammate's identity. Study personnel will instruct all pairs who are present to complete a Teammate Support worksheet that asks teammates to share with each other their quit plan, including their smoking habits, how often they would like to discuss quitting with each other, and how they would like to encourage each other to quit smoking.

At the end of the meeting, participants will receive an inconvenience gift of 150 baht in cash or in kind, whichever the person prefers.

e. Follow-up assessments

Follow-up assessments will take place at each worksite approximately 3 months, 6 months, and 12 months after the enrollment meeting. The date will be set in consultation with human resources or the health officer at the worksite. All participants will be contacted by phone during the week of the follow-up meeting to notify them of the upcoming visit.

Participants will complete two main activities during each follow-up assessment: a urine test and a follow-up survey.

We will use the COT One Step Cotinine Test, sold by Alfa Scientific Designs, an immunoassay that detects urine cotinine at a cutoff concentration of 200 ng/mL within about 10 minutes. The test was found to be easy to use and reliable during pre-testing.

Participants will be provided with a urine specimen cup, labeled with a unique ID number as they enter the restroom. Study personnel will stand outside of the restroom and will collect the full cup as each participant exits the restroom. The cups will be brought to a nearby designated room where testing will take place. The assessor of the biochemical urine test will be blinded to participants' randomization groups. The results of the urine test will be entered on a paper record and subsequently entered electronically. Following the follow-up survey described below, a trained smoking cessation counselor will share the urine test results with the participant and provide brief counseling.

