The primary outcome is biochemically-verified 7-day point-prevalence smoking abstinence obtained 12 months after enrollment, more than 9 months after all incentives were awarded. To be classified as having abstained, participants will have to self-report having abstained for the 7 days prior to the test and to test negative for nicotine and its metabolite cotinine using a rapid urine test. Participants who do not complete a survey or urine test will be assumed to be continuing smokers as part of the intent-to-treat analysis, as is the standard practice in the literature.⁵² At each end point, we will record whether the participant indicated active use of nicotine replacement therapy or e-cigarettes to aid in smoking cessation. In awarding incentives and in analyses, users of nicotine replacement therapy or e-cigarettes who reported smoking abstinence were treated as abstinent.

Secondary end points include biochemically verified 7-day point-prevalence abstinence at 3 months (end of intervention) and at 6 months (3 months after the incentives end). Another secondary outcome will be program take-up of interventions, defined as attending the on-site enrollment meeting, consenting to enter the trial, and if applicable, making at least the minimum deposit contribution.

7. Data management

The investigators are responsible for ensuring the accuracy, completeness, legibility, and timeliness of the data reported. All source documents will be completed in a neat, legible manner to ensure accurate interpretation of data.

Data collection and accurate documentation are the responsibility of the study staff under the supervision of the PIs. All source documents must be reviewed by the study team and data entry staff, who will ensure that they are accurate and complete.

Survey data will be collected electronically through Qualtrics. Data on outcomes assessment will be recorded on paper and subsequently entered electronically.

The crosswalk with personal identifiers will be transferred to the PI at the termination of fieldwork; the copy in Thailand will then be destroyed, and the PI will retain it for up to one year following the end of the study in case a scientific need arises for follow-up. Deidentified electronic files will be retained indefinitely.

8. Statistical considerations

a. Sample size and statistical power

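### Reported NRT or e-cigarette users count as abstinent even with a positive cotinine test, and the one planned check excludes them instead of classifying them by their result

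*Combined protocol and SAP*

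**What the plan says.** Section D.6 sets a two-part rule for abstinence: a 7-day self-report, and the participant must "test negative for nicotine and its metabolite cotinine using a rapid urine test". It then makes an exception, applied both to incentive awards and to analyses: "users of nicotine replacement therapy or e-cigarettes who reported smoking abstinence were treated as abstinent". Section D.8.b carries the exception into the primary outcome variable, which it still describes as verified, "treating reported NRT or e-cigarette use for cessation as abstinent as long as no cigarettes were used".

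The only assay, in section D.4.e, is "an immunoassay that detects urine cotinine at a cutoff concentration of 200 ng/mL within about 10 minutes". Product use comes from the participant's own account: "we will record whether the participant indicated active use of nicotine replacement therapy or e-cigarettes". No second marker and no proof of product use is described.

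One planned analysis addresses these participants. It is among the sensitivity analyses in section D.8.b: "Third, we will exclude from the analysis the outcome data from participants who reported currently using NRT or e-cigarettes".

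**The concern.** For a test-positive user, both the product use and the absence of smoking rest on the participant's word. That matters most where the motive to report use differs by arm. At 3 months the same rule decides payment. A bonus arm has 600 or 1,200 baht at stake, a deposit arm has the participant's own money, and in a team bonus arm a teammate's payment also depends on the answer. A control participant gains nothing from being classed as abstinent. Blinding the urine assessor does not protect a self-report.

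Any difference between arms in wrongly accepted claims passes directly into the risk difference. Excess accepted claims at 3 months could also look like relapse in the planned comparison of relapse after the incentive period.

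The planned check would not settle the matter. On its natural reading it selects on behaviour after randomization that the arm may influence. It also removes two groups whose status is not in doubt under the base rule: users who tested negative, and users who admit smoking.

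**Working it through.** **Step 1. What the exception does.** Take a participant who reports abstinence and product use. If the test is negative, the base rule is already met and the exception adds nothing. If it is positive, the base rule fails and the exception makes the participant a success. So the exception operates only on positive tests. A participant with no sample is a separate case: "Participants who do not complete a survey or urine test will be assumed to be continuing smokers". The text does not say whether that rule or the exception prevails for a user without a sample.

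**Step 2. Yardstick.** The plan gives no figure for this point. Section D.8.a gives a control rate of 6.0% and a detectable difference of 7.5 points. For 6.0% against 13.5%, two-sided alpha 0.05 (sidedness assumed) and 80% power, the pooled z formula needs 245 per arm without clustering. About 11 worksites of 60 give 660 per arm. The design effect that fits is 660/245 = 2.69, so the implied intraclass correlation is (2.69 − 1)/59 = 0.029, or about 0.025 with a t reference. The plan states no such value, so 7.5 points serves only as a scale.

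**Step 3. Effect on the primary rule.** Let t be the true abstinence rate and q the share of true non-abstainers accepted on a claim. The observed rate is t + (1 − t)q. With no true effect and t = 6.0% in both arms (all q assumed):

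- q = 0.5% control, 2% incentive: 7.88% − 6.47% = 1.41 points.
- q = 1% control, 3% incentive: 8.82% − 6.94% = 1.88 points.
- q = 0% control, 3% incentive: 8.82% − 6.00% = 2.82 points.

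**Step 4. Three ways to handle users.** Let n be the arm size, a the test-negative abstainers, k those among them who use a product, u the test-positive users accepted on report, and s the admitted smokers who use a product.

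- Primary rule: (a + u)/n
- Test-based, everyone kept: a/n
- Planned exclusion, read as dropping people: (a − k)/(n − k − u − s)

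All counts below are assumptions.

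*Set A*, n = 667 (6,000/9). Incentive: a = 60, k = 5, u = 20. Control: a = 40, k = 2, u = 5, s = 20.

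- Primary: 80/667 − 45/667 = 5.2 points.
- Test-based: 60/667 − 40/667 = 3.0 points.
- Exclusion, control: 38/640 = 5.94%. Incentive: 55/622 = 8.84%, 55/582 = 9.45% or 55/542 = 10.15% for s = 20, 60 or 100. Differences: 2.9, 3.5 and 4.2 points.

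*Set B*, n = 660. Incentive: a = 89, u = 13. Control: a = 40, u = 3.

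- Primary: 102/660 − 43/660 = 8.94 points.
- Test-based: 89/660 − 40/660 = 7.42 points.
- Exclusion, claimants only (k = s = 0): 89/647 − 40/657 = 7.67 points.
- Exclusion with k = 8 and 2, and s = 10 in each arm: 81/629 − 38/645 = 6.99 points.

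The exclusion lies above the test-based figure in some cases and below it in others. Which way it falls depends on k and s, and neither says anything about whether the claims are true.

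**The case against.** The exception is disclosed and has a sound reason. Nicotine products can turn a cotinine test positive, so a positive result in a user does not show smoking. The plan also prespecifies a check, and that check often works. In Set A with 20 admitted smokers who use a product in each arm, it gives 2.9 against 3.0. In Set B with claimants only, it removes (8.94 − 7.67)/(8.94 − 7.42), about 84% of the gap. About half the gap survives only in the most extreme case of Set A (100 against 20), and nothing in the plan explains such an imbalance: usual care is the same in every arm and no listed component supplies NRT.

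The background section says that 90% of Thai smokers attempting to quit use no cessation aid. The incentive arm in Set A has 45, 85 or 125 reported users out of 667 (6.7%, 12.7% or 18.7%). Only the first is under the roughly 10% that this implies, and there the check does well. The figure is background and not trial data, and reported use could exceed real use, but it is the only anchor available.

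There are other safeguards. The test result is shared only after the survey, and nothing says that participants are told of the exception. A reader might infer that someone could turn a known failure into payment. The documents do not support that: a participant would have to expect to fail and also know the rule.

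These points limit the size of the concern and argue against replacing the planned check. They do not remove the gap: no planned analysis keeps everyone in the denominator and classifies users by their test. The wording of the check also leaves some doubt whether excluded users leave the denominator, though that is the natural reading.

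**Conclusion.** The point holds as a matter of definition. At 3, 6 and 12 months some participants may be counted as verified on self-report alone, and the planned check cannot show reliably how much this matters. It is an inexpensive improvement worth making, not a flaw that undermines the trial.

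The size is unknown. Under the assumed counts the primary and test-based results differ by 2.2 points in Set A and 1.5 in Set B. With no true effect, the assumed claim rates give spurious differences of 1.4 to 2.8 points. Every one of these figures depends on user counts or claim rates that the documents do not supply.

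Three stronger readings go too far. A reader might infer that the 12-month primary result is inflated by claims made for money. Incentives end more than 9 months before that endpoint, and nothing in the documents shows that the 3-month motive carries over. A reader might infer that the planned exclusion always leaves the effect overstated, but it can land below the test-based figure (6.99 against 7.42). A reader might also take the test-based result as the true one. It misclassifies genuine users who have stopped smoking, and if incentives prompt such quitting it is itself uneven between arms.

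**What to change.** - Keep the primary rule, but describe the outcome as biochemically verified except for reported NRT or e-cigarette users.
- Beside the planned exclusion, add a sensitivity analysis at 3, 6 and 12 months. Keep every participant in the denominator and count as abstinent only those who both report abstinence and test negative.
- Report, by arm and time point, the number of abstainers accepted with a positive test.

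Present the strict analysis as a conservative bound, not as a condition for drawing conclusions, because it undercounts genuine users who no longer smoke. The cost is a few sentences in the analysis plan: the urine result and reported product use are already recorded.
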